7. CONDUCT OF STUDY: METHODS AND PROCEDURES

7.1 ENROLLMENT

7.1.1 INFORMED CONSENT

A signed informed consent form must be obtained from each subject prior to performing any study procedures. No study related procedures or activities will be performed until each subject is fully informed and the consent form is signed and dated.

7.1.2 DERMATOLOGICAL EXAMINATION

A skin examination will be performed to ensure all subject meet inclusion/exclusion criteria.

7.1.3 STUDY PROCEDURES

The subjects will be screened for the inclusion and exclusion criteria prior to study enrollment. Only subjects who meet the requirements, have signed an informed consent, and have given a medical history will be entered into the study. All other subjects will be considered screening failures.

7.1.4 STUDY MATERIAL ADMINISTRATION

The subjects will use 1% clascoterone as marketed (Winlevi) on one randomized side of the face.

7.1.5 SCREENING PROCEDURES

Potential volunteers will be enrolled based on their ability to meet the inclusion/exclusion criteria required for study enrollment.

7.2 STUDY CONDUCT PROCEDURES

7.2.1 BASELINE

Female or male subjects with acne prone skin will be enrolled in this split face single site study evaluating the barrier effects of Winlevi. Subjects who sign consent and meet all inclusion criteria and none of the exclusion criteria will be enrolled at the baseline visit. Subjects will be asked to continue their own, self-selected cleanser and sunscreen throughout the 2-week study with equal application to both sides of the face. The sunscreen and cleanser must have been used for 30 days prior to study enrollment without difficulty. Subjects must apply Winlevi twice daily to the randomized right or left face. Women of child bearing potential will receive a urine pregnancy test.

Subjects will receive a compliance diary and the blinded study treatment product to be applied to the randomized half face following cleansing, every morning and evening. The assessing dermatologist investigator will be blinded as to which side of the face is receiving the Winlevi treatment. The dermatologist investigator and subjects will assess tolerability for each side of the face separately at each visit on a 5 point ordinal scale (0=none, 1=minimal, 2=mild, 3=moderate, 4=severe). Noninvasive TEWL and corneometry assessments of both sides of the face will be conducted. Subjects will be instructed to return to the research facility in 24 hours. A reminder text for compliance will be sent prior to the return visit.

7.2.2 24 HOURS

Subjects will return to the research center in 24 hours. The dermatologist investigator and subjects will assess tolerability for each side of the face separately at each visit on a 5 point ordinal scale (0=none, 1=minimal, 2=mild, 3=moderate, 4=severe). Noninvasive TEWL and corneometry assessments of both sides of the face will be conducted. Subjects will be instructed to return to the research facility at week 1. A reminder text for compliance will be sent prior to the return visit.

7.2.3 WEEK 1

Subjects will return to the research center at week 1. The dermatologist investigator and subjects will assess tolerability for each side of the face separately at each visit on a 5 point ordinal scale (0=none, 1=minimal, 2=mild, 3=moderate, 4=severe). Noninvasive TEWL and corneometry assessments of both sides of the face will be conducted. Subjects will be

instructed to return to the research facility at week 2. A reminder text for compliance will be sent prior to the return visit.

7.2.4 WEEK 2

Subjects will return to the research center at week 2. The dermatologist investigator and subjects will assess tolerability for each side of the face separately at each visit on a 5 point ordinal scale (0=none, 1=minimal, 2=mild, 3=moderate, 4=severe). Noninvasive TEWL and corneometry assessments of both sides of the face will be conducted. Women of child bearing potential will be administered a urine pregnancy test. Subjects will complete their study participation at week 2. The compliance diary and all study products will be collected at this time.

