6.3 INCLUSION CRITERIA

The following items represent the inclusion criteria:

- 1. Subjects who self identify as having sensitive acne prone skin.
- 2. Female or male subjects 18+ years of age.
- 3. Subjects with Fitzpatrick skin types I-VI.
- 4. Subject agrees not to introduce any new colored cosmetics (lipsticks, eye shadows, facial foundations, blush, powder) or skin care products during the study.
- 5. Subjects must be willing to use only a cleanser and sunscreen on the entire face and no other skin care products.
- 6. Subjects must be willing to use the Winlevi study product to designated half face. No other topical acne treatment products on the entire face for the 2 week duration of the study.
- 7. Subject has signed an Informed Consent Form in compliance with 21CFR Part 50: "Protection of Human Subjects."
- 8. Subject is dependable and able to follow directions and is willing to comply with the schedule of visits.
- 9. Subject is in generally good physical and mental health.

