8. EFFICACY MEASURES

8.1 STUDY MEASURES

Dermatologist Investigator assessed tolerability parameters: dryness, erythema, scaling, and irritation will be assessed separately for each side of the face. All assessments will be made on a 5-point ordinal scale (0=none, 1=minimal, 2=mild, 3=moderate, 4=severe) at baseline, 24 hours, week 1, and week 2.

Subject assessed tolerability parameters: dryness, tightness, stinging, itching, and burning will be assessed separately for each side of the face. All assessments will be made on a 5-point ordinal scale (0=none, 1=minimal, 2=mild, 3=moderate, 4=severe) at baseline, 24 hours, week 1, and week 2.

Noninvasive Biomeasurements: TEWL and corneometry measurements on the right and left cheek will be conducted at baseline, 24 hours, week 1, and week 2.

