10.3 STUDY PRODUCT ADMINISTRATION

The subjects will apply the study products twice daily to the randomized side of the face. The study products will be labeled left and right to ensure subject compliance. The subjects will receive the following instructions: Apply twice daily to entire randomized side of face (product applied to randomized forehead, cheek, and jawline).

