12.5 ENDPOINTS

12.5.1 PRIMARY EFFICACY ENDPOINT

The primary endpoint is the change in corneometry reading between the side of the face treated with Winlevi versus no treatment.

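### No rule separates the morning Winlevi application from the cheek readings, so product left on one cheek can enter the primary corneometry contrast

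*Combined protocol and SAP*

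**What the plan says.** **Application.** Section 7.2.1 has the product "to be applied to the randomized half face following cleansing, every morning and evening", with no exception for visit days. Section 10.3 defines the area: "product applied to randomized forehead, cheek, and jawline".

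**Measurement.** Section 8.1 states: "TEWL and corneometry measurements on the right and left cheek will be conducted at baseline, 24 hours, week 1, and week 2". The visit text adds one sentence, repeated at every visit (7.2.1 to 7.2.4): "Noninvasive TEWL and corneometry assessments of both sides of the face will be conducted". Neither place gives a clock time, an interval since the last application, or a skin preparation step. The Study Visit Schedule (section 2) has no such step, and the noninvasive assessment table in Appendix I has one cell per instrument, cheek and visit, with no time field.

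**Comparator.** Section 12.5.1: "The primary endpoint is the change in corneometry reading between the side of the face treated with Winlevi versus no treatment". There is no vehicle side.

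**Products common to both cheeks.** Subjects "continue their own, self-selected cleanser and sunscreen throughout the 2-week study with equal application to both sides of the face" (section 7.2.1). Moisturizers are excluded on both sides (section 6.4, exclusion 2).

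**Analysis.** Paired t-test (section 12), two-sided at 0.05 (section 12.2), 50 subjects chosen by the sponsor (section 12.1). The objective in section 4 is to show that Winlevi does not damage the barrier.

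**The concern.** The treated site is the measured site. A subject who follows the protocol exactly can arrive at 24 hours, week 1 or week 2 with that morning's cream still on one cheek and no counterpart on the other. A compliance reminder is texted before each return visit, which if anything makes a recent application more likely. The reading then reflects the skin plus whatever product is on it.

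The primary endpoint carries this directly. If residual cream raises a hydration reading, a real loss of hydration on the treated side could be hidden, or a null effect could appear as a benefit. Either would support the conclusion the study sets out to reach. No margin for lack of damage is specified, so a non-significant paired test would probably be read as success. Masking therefore helps the claim.

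**Working it through.** **1. What the contrast contains.** Let T and U be the treated and untreated cheeks. The primary quantity per subject is

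D = (T_post − T_base) − (U_post − U_base).

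Let s be any additive contribution common to both cheeks at a visit (sunscreen, cleanser residue, room conditions), and f the contribution of residual Winlevi, present only in T_post. The s terms cancel between cheeks. Product is first dispensed at the baseline visit, so I take T_base as read without it; f is then not subtracted. Hence D = true side difference + f. Randomising the side and blinding the assessor leave f in place, since f follows the treatment.

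**2. The plan's own figure.** The sample size of 50 cannot be reproduced: no effect size, SD, power or margin is given. No stated figure is contradicted.

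**3. Scale, by assumption.** Inputs from the documents: n = 50, paired t-test, two-sided 0.05. Assumed: all 50 evaluable, a true loss of 0.40 SD of D, and a constant opposing shift b in the same units. The 0.40 is chosen because 0.404 SD is what n = 50 detects with 80% power.

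Power to find damage = P(t′ > t_crit), with t′ noncentral t on 49 df, noncentrality (0.40 − b)√50 and t_crit = 2.01. Values were checked by simulation with 100,000 runs per point and agreed within 0.3 percentage points.

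| Shift b (SD) | Net loss (SD) | Noncentrality | Power to find the loss | Chance of missing it |
|---|---|---|---|---|
| 0 | 0.40 | 2.83 | 79% | 21% |
| 0.1 | 0.30 | 2.12 | 55% | 45% |
| 0.2 | 0.20 | 1.41 | 28% | 72% |
| 0.3 | 0.10 | 0.71 | 10% | 90% |
| 0.4 | 0 | 0 | 2.5% | 97.5% |

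**4. No true effect.** With noncentrality b√50, the chance of a significant apparent hydration benefit is 10%, 28%, 55% and 79% for b = 0.1, 0.2, 0.3 and 0.4, against 2.5% with no shift.

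**5. Sample size does not help.** With no true effect and b = 0.2, the false-benefit rate is 28% at n = 50 (noncentrality 0.2√50 = 1.41) and 51% at n = 100 (0.2√100 = 2.00).

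**The case against.** **The effect may be intended.** The Introduction (section 3) credits the vehicle with barrier properties of its own and speaks of positive barrier effects, and the product is tested as marketed against no treatment. The sponsor could say that hydration with product in place is the target. This stands in part: the protocol never says which effect is meant, while the objective in section 4 points to the barrier itself. Even under the in-use reading, an uncontrolled interval would mix recent and hours-old applications.

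**Direction and size are not in the documents.** This stands. No section describes the device, the vehicle's composition or how long residue lasts, and visit clock times are not given. A reader might infer that the result *will* be biased in the sponsor's favour; the documents support only that it *can* be.

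**The diary may hold times.** Subjects record applications there (section 8.2), and it is checked at each post-baseline visit. It is a separate file and could contain clock times or a visit-day instruction. What can be said is that the protocol and the CRF table contain neither.

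**Stronger readings that fail.** A reader might picture the untreated cheek as free of any product. It is not: sunscreen and cleanser are used equally on both sides, and their contribution should largely cancel. A reader might also count the absence of an acclimatisation period as one-sided bias. It affects both cheeks alike, so it is mainly a matter of precision. The same holds for any cosmetics already in use; inclusion 4 bars only new ones ("Subject agrees not to introduce any new colored cosmetics"), but nothing places them on one side.

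**A wash has its own costs.** It could conflict with the unchanged-cleanser rule in exclusion 2, take off the visit-day application, or itself alter the reading. These points shape the fix; they do not remove the problem.

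**Conclusion.** The point holds as a gap in the measurement conditions for the primary and secondary endpoints. Followed exactly, the protocol can place a product effect on one side of the primary contrast, and the analysis cannot separate it afterwards without recorded times. For corneometry the likely direction is towards no damage, on the assumption that a residual cream layer raises the reading. For TEWL the direction is uncertain.

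The power figures show sensitivity only. They rest on an assumed true loss of 0.40 SD, an assumed constant shift and full follow-up. They do not show that a shift of any given size would occur in this trial. The sponsor should act, since the remedy is cheap and missing times cannot be recovered later.

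**What to change.** 1. In sections 7.2 and 8.1, state whether the target is the skin barrier itself or hydration with product in place, consistently with section 4.
2. Set one measurement condition, identical for both cheeks and for all visits including baseline. It can be either a stated minimum interval since the last application of any product, or the same cleansing of both cheeks with the subject's own unchanged cleanser followed by a fixed wait. The sponsor should choose the condition and reconcile it with the twice-daily application instruction and exclusion 2; no interval is proposed here.
3. Add the time of last Winlevi use, the time of last sunscreen use and the time of reading to the noninvasive assessment CRF.
4. If an interval rather than a wash is chosen, pre-specify a sensitivity analysis of the side difference by time since last application. After a wash of both cheeks it would add little.

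Cost: a short amendment with sponsor and IRB approval (section 14.4), a few CRF fields and slightly longer visits. No extra subjects are needed.

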8. EFFICACY MEASURES

8.1 STUDY MEASURES

Dermatologist Investigator assessed tolerability parameters: dryness, erythema, scaling, and irritation will be assessed separately for each side of the face. All assessments will be made on a 5-point ordinal scale (0=none, 1=minimal, 2=mild, 3=moderate, 4=severe) at baseline, 24 hours, week 1, and week 2.

Subject assessed tolerability parameters: dryness, tightness, stinging, itching, and burning will be assessed separately for each side of the face. All assessments will be made on a 5-point ordinal scale (0=none, 1=minimal, 2=mild, 3=moderate, 4=severe) at baseline, 24 hours, week 1, and week 2.

Noninvasive Biomeasurements: TEWL and corneometry measurements on the right and left cheek will be conducted at baseline, 24 hours, week 1, and week 2.

8.2 SUBJECT COMPLIANCE

The diary sheets will be used to determine compliance. Subjects will record product application and any comments on the provided weekly diary. Diary sheets will remain at the study center as part of the source documentation records.

8.3 NONCOMPLIANT SUBJECTS

Subjects who are found to be noncompliant will be queried as to the reason for their noncompliance. If noncompliance results from study product problems, full interviews will be conducted by the investigator to determine the nature and severity of the problem and an adverse event will be recorded. Subjects who are noncompliant will be released from their study participation and their last visit data carried forward.

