2. STUDY VISIT SCHEDULE

	Visit 1	Visit 2	Visit 3	Visit 4
Procedures	BL	24 Hours	Week 1	Week 2
Informed Consent Procedure	X			
Inclusion/Exclusion Criteria	X			
Brief Medical History and Concomitant Medications Review	X	X	X	X
Investigator Clinical Grading for Tolerability	x	X	X	x
Subject Clinical Grading for Tolerability	x	X	X	Х
Product Dispensing	X			
TEWL (both facial sides)	x	X	X	X
Corneometry (both facial sides)	x	X	X	X
Urine Pregnancy Test (WOCP)	x			Х
Adverse Events		X	X	X
Subject Diary Assessment and Compliance Check	S R	x	X	х
Subject Product Accountability and Study Completion				х

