9.1 COMPLETED, DISCONTINUED OR INCOMPLETE SUBJECTS

A completed subject is a subject who has satisfied all study entry criteria and completed the 2-week study. For any subject who has started study and terminates the study prematurely, efforts will be made to obtain final evaluations of clinical status. Reasonable efforts will be made to contact any subject lost to follow-up during the course of the study in order to complete assessments and retrieve any outstanding data and clinical supplies. The investigator will choose the description that best describes the status of the subject at termination.

1. Subject completed the 2-week study period

OR INCOMPLETE/DISCONTINUED DUE TO:

- 2. Contact dermatitis
- 3. Adverse experience
- 4. Serious adverse experience
- 5. Pregnancy
- 6. Protocol violation
- 7. Subject withdrew consent
- 8. Subject lost to follow-up
- 9. Other

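### Section 8.3 releases every noncompliant subject and carries the last reading forward, with no exit corneometry or TEWL specified, so an earlier and possibly pre-damage reading can stand in for the one that matters

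*Combined protocol and SAP*

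**What the plan says.** Section 8.3 covers all noncompliance in one sentence: "Subjects who are noncompliant will be released from their study participation", and that sentence goes on to carry the last visit's data forward. Where product problems are the cause, the same section asks that "full interviews will be conducted by the investigator to determine the nature and severity of the problem and an adverse event will be recorded"; it does not ask for an instrument reading. Section 8.2 judges compliance from the diary and sets no threshold.

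Section 9.1 says that for a subject who ends the study early, "efforts will be made to obtain final evaluations of clinical status". It adds: "Reasonable efforts will be made to contact any subject lost to follow-up during the course of the study in order to complete assessments". Neither sentence names corneometry or TEWL. Section 12.3 adds a side-effect query for subjects who discontinue.

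Section 8.1 fixes the instrument readings: "TEWL and corneometry measurements on the right and left cheek will be conducted at baseline, 24 hours, week 1, and week 2". The table in section 2 and the noninvasive page in Appendix I have those four columns and no other.

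**The concern.** The objective (section 4) is to demonstrate that the product does not damage the barrier. Section 3 itself connects acne medication with dryness, barrier damage and poor compliance, and section 9.1 lists contact dermatitis among the exit reasons. On the protocol's own reasoning, product-related noncompliance may be related to the outcome being measured.

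A rule that ends scheduled measurement on noncompliance and substitutes the last reading can therefore replace a post-damage value with a pre-damage one. For those subjects the error runs toward the conclusion the trial hopes to reach. A reading that was never taken cannot be recovered in the analysis, so this has to be settled before the study is run. The site cannot simply improvise either, because section 14.4 bars deviations without an approved revision.

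**Working it through.** **1. The sections side by side**

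| Question | 8.3 | 9.1 | Section 2, 8.1 and CRF |
|---|---|---|---|
| Who leaves? | All noncompliant subjects, whatever the reason | Anyone ending early | – |
| Corneometry or TEWL at exit? | Not mentioned | Not named; efforts at a clinical evaluation | No exit column |
| Readings after release? | None; last visit's data carried forward | Completing assessments is mentioned only for those lost to follow-up | Planned visits only |
| Is measurement done before release? | Not stated | Not stated | Compliance check and both instruments share the 24-hour, Week 1 and Week 2 visits |

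The last row matters. A subject found noncompliant at a visit may be measured that day, but the text does not require it. A subject who stops and reports between visits has no provision for a reading at all. If trouble starts after the 24-hour visit and release precedes any Week 1 reading, the 24-hour value becomes the Week 2 value.

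**2. The plan's own figure**

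The sample size of 50 (section 12.1) is the sponsor's choice, with no effect size, SD, margin, power or dropout rate. It cannot be reproduced, and no exit rate is available. Section 12.5 names no time point for either endpoint; Week 2 is assumed here. Everything below is illustrative.

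**3. Size of the understatement**

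Let p be the share released, d the size of their true treated-versus-untreated deficit, and λ the fraction of d already present in the carried-forward reading. The contribution to the mean is p × d if measured and p × λ × d if carried forward, so

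understatement = p × d × (1 − λ).

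| p (of 50) | d, units | λ = 0 | λ = 0.5 | λ = 1 |
|---|---|---|---|---|
| 2% (1 subject) | 5 | 0.1 | 0.05 | 0 |
| 10% (5 subjects) | 10 | 1.0 | 0.5 | 0 |
| 20% (10 subjects) | 15 | 3.0 | 1.5 | 0 |

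**4. Effect on the paired t-test**

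The inputs are n = 50, two-sided α = 0.05 (section 12.2) and a noncentral t calculation. Effects are in units of the SD of the side difference, which is held the same in each scenario. Let Dc be the difference in retained subjects and Dr that in released subjects, both assumed.

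- Dc = −0.2, Dr = −1.0, p = 10%. All measured: 0.9 × (−0.2) + 0.1 × (−1.0) = −0.28, power 0.49. Carried forward with λ = 0: −0.18, power 0.24.
- Dc = −0.2, Dr = −1.5, p = 20%. All measured: 0.8 × (−0.2) + 0.2 × (−1.5) = −0.46, power 0.89. Carried forward with λ = 0: −0.16, power 0.20. With λ = 0.5: −0.16 + 0.2 × 0.5 × (−1.5) = −0.31, power 0.575.
- With λ = 1 nothing is lost in either case.

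The second case is deliberately severe. It shows that the rule can matter, not that it will.

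**The case against.** The case on the other side has real force.

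- **Compliance checks fall at visits where both instruments are due.** This is the best argument, and it narrows the gap to subjects who stop between visits and do not return, subjects released before that day's readings, and visits after release. It does not close the gap, because the order of measurement and release is unstated.
- **Released subjects stay in the analysis.** A reader might infer that they leave unmeasured, or that the Week 2 result describes only those who tolerate the product. The documents do not support either: earlier readings exist and are carried forward.
- **Contact does not end.** A reader might infer that it does. But section 11.2.1 follows subjects withdrawn for an adverse event until the outcome is determined, section 12.3 queries those who discontinue, and section 9.1 calls for efforts at a final evaluation. None of these names corneometry or TEWL.
- **The bias is not always toward no damage.** It is zero at λ = 1. If skin recovers after stopping, a carried-forward reading could show more damage than a true Week 2 reading, which reverses the sign. Noncompliance unrelated to the product is released under the same rule and need not bias the result. Section 8.3 does not single out subjects whom the product bothered.
- **Continued measurement has its own cost.** Off-product readings pooled with the rest could also move the mean toward no difference. This stands, and the fix has to deal with it.

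**Conclusion.** The concern holds in limited form. Release of all noncompliant subjects is mandatory, no exit corneometry or TEWL is specified, and sections 8.3 and 9.1 do not say together what is measured when a subject stops. Subjects with product problems may therefore lack an exit or Week 2 reading, and an earlier one stands in.

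The understatement is p × d × (1 − λ): 0 to 1.0 unit for p = 10% and d = 10 units, and 0 to 3.0 units across p = 2–20% and d = 5–15 units. All of these inputs are assumed. The direction favours the objective only where released subjects have a deficit that their last reading did not fully capture. This is a weakness worth repairing cheaply; the documents do not show that the result will be biased.

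**What to change.** Reconcile 8.3 with 9.1 by separating stopping the product from leaving the study.

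- In 8.3, state that corneometry, TEWL and both tolerability scales are taken on both sides before any release at a visit, or at an exit assessment if the subject can attend.
- State that subjects who do not withdraw consent are still measured at the remaining planned visits, whatever their product use.
- Add an early-termination column to the section 2 table and to the noninvasive CRF page, with the same instruments named in 9.1.
- Record the date of last application.
- Report on-product and exit readings separately from off-product readings, because skin off product may have recovered, and do not rely on carry-forward alone.

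The cost is a short amendment, a few extra exit readings for subjects who stop between visits, and some off-product data to label. No new equipment is needed. This concerns measurement only; it proposes no rule on whether anyone continues or stops the product.
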